Buprenorphine Plus Baclofen to Increase Analgesia in Healthy Volunteers

NCT04251819

November 14, 2025

Statistical Analysis Plan

All baseline characteristics and outcome measures were analyzed descriptively. Specifically, the means and standard deviations within each group (i.e., Placebo, Baclofen 5mg, and Baclofen 10mg) were calculated for all continuous variables. For the baseline characteristic of age, the mean and standard deviation of the overall sample was also calculated. For the categorical variables, frequencies of each category within each group and in the overall sample were calculated. No analyses were conducted to compare the groups on any variable.

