Baclofen is a GABA receptor agonist that is FDA-approved to treat spasticity. Baclofen has an established clinical safety profile, as well as evidence to support its use in addictions, primarily with alcohol use disorders. Our preclinical evidence suggests baclofen, in combination with buprenorphine, increases the analgesic effects of buprenorphine in rodents. Using these medications together may offer an important novel strategy to increase retention in treatment and adherence to buprenorphine while preserving the safety profile of a partial opioid agonist, particularly among patients with a chronic pain condition who may be more likely to abuse illicit opioids. However, data for this approach in humans is lacking and initial evidence is needed to assess the analgesic interaction, safety, acceptability and feasibility of using buprenorphine and baclofen in humans before conducting a larger clinical trial to examine efficacy in patients.

Brief purpose of the study

The purpose of the study is to determine if baclofen will enhance buprenorphine analgesia for acute pain in healthy volunteers (non-opioid users). We will first recruit 30 healthy volunteers (Group 1) who will be administered either 4mg of Buprenophine, 5 mg of Baclofen, or 10 mg of Baclofen in order to test the effects of the drugs on pain separately.

Then, we will recruit another 60 healthy volunteers (non-opioid users; Group 2) and randomize them to either placebo, 5mg or 10 mg of baclofen (1 dose) in combination with 4 mg of buprenorphine to examine analgesia in acute pain tasks.

Measurement occurrence

Data Collection Instrument	Session 1	Session 2
Informed consent	✓	
Screening questions (survey)	✓	
Vital signs: blood pressure, heart rate, temperature, neck circumference, height/weight	✓	✓
Blood draw	✓	✓
Pregnancy test		✓
Urine drug screen		✓
Demographics questionnaire (survey)		✓
Profile of Mood States Questionnaire (POMS) (survey)	✓	✓
QST: Cold pressor task	✓	
QST: Heat pain task	✓	✓
QST: Cold pain task	✓	✓
QST: Mechanical pressure pain task	✓	✓
QST: Conditioned pain modulation task	✓	✓
QST: Pinprick pressure pain task	✓	✓
26-item Visual Analog Scale (VAS) (survey)		✓
Drug Effects Questionnaire-5 (survey)		✓
Opioid symptom checklist		✓

Accessing the shared drive

1. Click on the home button at the bottom left hand of the computer
2. Go to “Computer”
3. Click on “PBN.” Enter your blazer ID and password if necessary
4. Click on “[name]-Lab”

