Participants will then complete the POMS and the Opioid Symptom Checklist prior to taking the study drug. These questionnaires will be entered directly into REDCap by the participant as a survey. Then, alert the nurse that you are ready for them to give the pt the study drug. Note that it can sometimes take up to an hour for the nurse to retrieve the drug from the pharmacy, so you may have to wait a little bit.

Then participants will be administered the study drug:

- First cohort (n=30): Randomized to either 5 mg of baclofen, 10 mg baclofen ,or 300 mcg of buprenorphine (n=10 per group). **All participants in this cohort will receive one dose of one single drug compound.**
- Second cohort (n=60): Randomized to 300 mcg of buprenorphine, and either: placebo, 5 mg of baclofen, or 10 mg of baclofen (n=20 per group). **All participants in this cohort will receive a combination of drug compounds.**

Participants will be instructed to take the drug(s) orally (baclofen) or buccally as a film (buprenorphine). Following the administration of the study drug, all study procedures are identical for all groups and cohorts.

Visit timeline

The visit timeline for session 2 is as follows (represented below in 15-minute segments):

Group 1 (single compound)

-1	0	15	30	45	1 hr	15	30	45	2 hrs	15	30	45	3 hrs
Vitals, surveys, OSC	Adm drug OSC	Vitals	Vitals, blood draw #1, surveys	...	Vitals OSC	...	QST	...	Vitals, OSC	...	Blood draw #2	...	Vitals, OSC
Begin 3 hour post-dose observation End observation													

Group 2 (duo compound)

0	15	30	45	1 hr	15	30	45	2 hrs	15	30	45	3 hrs	15	30	45	4 hrs
Vitals Surveys OSC	Adm Bup OSC	Vitals	Adm Bac	...	Vitals, blood collection	Surveys	Vitals OSC	...	QST	...	Vitals OSC	Vitals OSC
Begin 3 hour post-dose observation End observation																

Participants are asked to stay for a 3-hour observation period post-drug administration as that is the amount of time it typically takes for the drug(s) to leave their system. This observation period will allow us to monitor the side effects of the medications while it is still in their system. During the observation period, participants' vital

signs will be taken periodically to monitor drug side effects. We will also administer the Opioid Symptom Checklist at various timepoints to quantify the drug's effects.

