The research staff running the session will also periodically administer the Opioid Symptom Checklist (OSC). This questionnaire will be administered pre-drug administration, at the time of first drug administration, 1 hour post-drug administration, 2 hours post-drug administration, and 3 hours post-drug administration.

- **Opioid Symptom Checklist (OSC):** A 13-item scale used to quantify any sedation, somnolence, and other drug effects that the participant is experiencing from the buprenorphine and/or baclofen. Participants answer true/false questions about these opioid effects. This checklist takes approx. 2 minutes to administer.

Post-observation period

Once the 3-hour observation period has concluded, and the participant has finished all the QST tasks and questionnaires, they will be free to leave. Make sure they are not experiencing any severe side effects before allowing them to leave. If they are still feeling sick, allow them to wait a bit before leaving. Because we are giving them a drug known to produce somnolence as a side effect, participants will not be allowed to drive home and must have someone pick them up from their visit. If they are not able to have someone drive them home from the visit, we will arrange for an Uber Health taxi to bring them home (free of charge to the participant).

Post-visit procedures

Following the study visits, enter all data into REDCap that was recorded on paper forms. Also be sure that the urine drug screen and pregnancy test results are entered into REDCap. Update the participant tracking SPSS database (P:\[name]-Lab\BACUP\6. Databases → BACUP Participant Tracking).

Adverse event procedures

In the event that a participant has severe side effects from the study medication or procedures, the study doctor and PIs should be alerted as soon as possible. Examples of severe adverse side effects would be vomiting, blood pressure reading that is too high/too low, sudden spike or drop in body temperature, etc. If any of these occur, first alert one of the CRU nurses so that they can come check on the pt. Then, call the study doctor to let them

know what occurred. You can also have the CRU nurse talk to them so that they can relay treatment information to the nurse.

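### The SAP names no safety variable and plans no count by regimen of adverse events or out-of-range vital signs; at 20 per arm, means and SDs can hide isolated reactions

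*SAP*

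**What the plan says.** The manual's Introduction states that "initial evidence is needed to assess the analgesic interaction, safety, acceptability and feasibility of using buprenorphine and baclofen in humans" before a larger trial in patients. The section on the study's brief purpose is narrower: "The purpose of the study is to determine if baclofen will enhance buprenorphine analgesia for acute pain in healthy volunteers".

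Under Visit timeline (study session 2), participants stay for 3 hours after dosing so that side effects can be watched, and their vital "signs will be taken periodically to monitor drug side effects". The Opioid Symptom Checklist (OSC), 13 true/false items, is given before dosing, at first dosing, and 1, 2 and 3 hours later.

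The section Adverse event procedures opens with "In the event that a participant has severe side effects from the study medication or procedures". It then describes alerting staff, a follow-up call the next day and a problem report to the IRB. The session 2 text also tells staff to notify a nurse if blood pressure or heart rate goes out of range.

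The SAP is one paragraph covering baseline characteristics and outcome measures. For continuous data, "the means and standard deviations within each group (i.e., Placebo, Baclofen 5mg, and Baclofen 10mg) were calculated for all continuous variables". Categorical variables get frequencies by group and overall, and groups are not compared. Adverse events, vital signs and the OSC are not named.

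**The concern.** In a first human study of a drug combination, the useful safety result is how many people on each regimen had a reaction, and how large the worst reactions were. The study collects much of what is needed for this, but the analysis plan never asks for it. Events are handled one at a time, through the bedside response and an individual IRB report, and no step adds them up by regimen. The manual's Measurement occurrence table lists vital signs and the OSC but no adverse-event form.

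A mean with an SD is a poor summary for this purpose, because one or two people with a marked fall in blood pressure are diluted by the rest of the arm. A team planning the next trial could read unremarkable arm means without learning how many participants had an event.

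**Working it through.** The documents give no SD, event rate, size of fall or safety threshold, so there is no design figure to reproduce. Only the arm sizes can be checked, and they agree with the cohort totals.

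**Inputs from the manual (study session 2)**
- Cohort 2, all on buprenorphine: "either: placebo, 5 mg of baclofen, or 10 mg of baclofen (n=20 per group"; 3 × 20 = 60.
- Cohort 1, single drug: "Randomized to either 5 mg of baclofen, 10 mg baclofen ,or 300 mcg of buprenorphine (n=10 per group"; 3 × 10 = 30.

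**Inputs assumed**
- A marked fall in systolic pressure of 30 to 40 mmHg in an affected person.
- A background SD of 8 to 15 mmHg.

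**1. Shift in the arm mean.** Shift = k × fall / n, where k is the number affected and n = 20.
- k = 1: 30/20 = 1.5 to 40/20 = 2.0 mmHg.
- k = 2: 60/20 = 3.0 to 80/20 = 4.0 mmHg.

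**2. Yardstick.** The SAP makes no comparison, so the standard error of a difference between two arms stands in for the noise a reader would allow for. SE = SD × √(2/n).
- SD 8: 8 × √(2/20) = 2.5 mmHg.
- SD 15: 15 × √(2/20) = 4.7 mmHg.
- One affected person: 1.5/4.74 = 0.3 to 2.0/2.53 = 0.8 SE, so below 1 SE throughout.
- Two affected people: 3.0/4.74 = 0.6 to 4.0/2.53 = 1.6 SE.

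**3. Does the SD give it away?** Reported SD = √(SD² + p(1 − p) × fall²), where p = k/n.
- 2 of 20 with a 30 mmHg fall, SD 8: √(64 + 0.1 × 0.9 × 900) = √145 = 12.0. The arm reads −3 ± 12 against 0 ± 8.
- 4 of 20 with a 40 mmHg fall, SD 12: the mean moves by 8 mmHg and the SD becomes √(144 + 0.2 × 0.8 × 1600) = √400 = 20. That would be noticed.

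**4. What counts would show.** At n = 20 each affected person is 5 percentage points. Exact two-sided 95% limits:
- 0/20: upper limit 1 − 0.025^(1/20) = 16.8%.
- 0/10: upper limit 1 − 0.025^(1/10) = 30.8%.
- 2/20: 1.2% to 31.7%.

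If the true rate were 5%, the chance of at least one event in 20 people is 1 − 0.95^20 = 64%. Counts make events visible, but they are not a powered test. For assumed rates of 5% and 25% with 20 per arm, power is about 42% (two-sided 0.05, normal approximation).

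**The case against.** The best defence is that the documents do more about safety than a quick reading suggests. Several stronger conclusions that a reader might draw are not supported.

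- *Safety is an aim of the study.* It appears in the Introduction as evidence that is needed. The purpose section names analgesia only.
- *The SAP averages the vital signs.* It does not mention them. That would follow only if they count as outcome measures, and the documents do not say whether they do.
- *No symptoms would be counted by arm.* If the OSC is an outcome measure analysed by item, the rule for categorical variables gives symptom frequencies by group. The 26-item visual analog scale and the Drug Effects Questionnaire also capture drug effects.
- *Nothing happens short of a severe event.* Staff must also act on out-of-range blood pressure or heart rate. The adverse-event section counts vomiting and abnormal blood pressure among its examples of severe effects, so a marked fall could well be escalated and reported.
- *A harmful arm would look clean.* Step 3 shows that a frequent, large effect would move both the mean and the SD.

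All five corrections stand, but they leave the main gap open. Whether or not vital signs are outcome measures, no out-of-range count or worst value results. Symptom frequencies carry no severity and miss unlisted events. Escalation protects the individual but produces no cumulative figure by regimen. The blank data sheets are not in the documents and may record more events, but the SAP would still have no rule for counting them.

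**Conclusion.** The point holds in a limited form. The SAP names no safety variable and asks for no count by regimen of adverse events or out-of-range vital signs, although the manual gives safety evidence as part of the rationale and sets aside 3 hours to monitor side effects. The summaries it does specify can hide one or two marked reactions in an arm of 20, with a shift of at most about 1.6 SE over the range examined. The masking figures rest on the assumed falls and SDs. The absence of a safety count rests on the text alone. The gap leaves the report of the study incomplete. It does not show that any arm was harmful or that participants were unprotected. The sponsor should correct it, because most of the data needed are already collected.

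**What to change.** Add a safety table by regimen to the SAP. It should cover the three cohort 2 arms and the three cohort 1 arms, including buprenorphine alone, which the SAP's group labels omit. For each regimen give:

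- the number (%) of participants with any recorded adverse event or problem report;
- the number (%) with vomiting;
- the number (%) with any OSC item newly true since the pre-dose checklist;
- each participant's worst post-dose change in each vital sign, summarised by the median and extremes;
- the number (%) with any post-dose reading out of range.

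The study team must state the range used for the last item. The manual refers to out-of-range and abnormal readings after dosing without defining limits, and the 150/95 under study session 1 is an entry check.

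Give exact 95% limits with every count, including zeros. Label the table post hoc, because the SAP is dated November 2025 and written in the past tense.

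Logging side effects of every severity in REDCap would close the recording gap, but only for visits still to come or for a successor trial.

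The cost is one extra table, drawn mostly from existing data, and a little more recording at any future visit.

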Following eligibility determination, questionnaires, and blood draw participants will undergo a battery of pain tasks (see "[Pain tasks](#)" section for more information). Once the pain tasks are completed, the participant's information will be added to ClinCard and they will be compensated \$50 for completing session 1. They will be asked to come back a week later (7 days \pm 2 days) to complete session 2, where they will receive a study drug and complete the pain tasks once again. Remind the participant of their visit 2 date at the end of visit 1.

[Study session 2 \(approx. 4 hours long – occurs 7 \$\pm\$ 2 days after session 1\)](#)

A couple days before the visit, make sure that the prescription (Rx) for the study drug has been emailed to the investigational pharmacy ([contact]). Specify which study the Rx is for (2738) and the date of the visit. If you are not sending the Rx from a uabmc.edu email, it is advised to fax the form rather than emailing it as the Rx form has a lot of PHI on it. The fax number is [ask [name]].

Before the visit, be sure to print out all the required paperwork:

- Blank visit 2 data recording sheet
- Visit 2 flow sheet (double check to make sure all information is accurate, i.e., DOB and visit date)
- Physician's order form (Rx order form) – this should also have been sent to the pharmacy prior to the visit
- CRU space request form (optional, but good to have on hand just in case there is an issue)

[figure not shown]
You will also need the following supplies:

- Urine drug test cup
- Pregnancy test (if female of child-bearing potential)
- Surface Pro and charger
- TSA laptop and charger
- Stopwatch
- Clipboard
- Pens

When participants arrive for session 2, they will repeat the same procedures as the beginning of visit 1 (BP/HR readings, temperature, weight). Then participants will be asked to complete a urine drug screen and a pregnancy test (if a participant is a woman of child-bearing potential). A positive drug or pregnancy test reading will result in immediate termination from the study (if they only test positive for THC they are allowed to continue)

- Pregnancy test: Hold strip vertically in urine sample for at least 5 seconds. Read results after 3 minutes.

- Urine drug screen: Have participant provide sample in urine drug screen cup. There must be enough urine to cover the black temperature indicator strip. Wait 2-4 minutes before removing the peel-off label, then wait another 5 minutes to read results.

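### The study asks whether baclofen enhances buprenorphine analgesia, but the SAP gives no between-arm difference or confidence interval and makes no described use of the Session 1 pain scores

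*SAP*

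**What the plan says.** The protocol (a manual of operations), under Brief purpose of the study, states: "The purpose of the study is to determine if baclofen will enhance buprenorphine analgesia for acute pain in healthy volunteers". Group 2 is the randomised test of that. Under Study session 2, its participants receive buprenorphine "and either: placebo, 5 mg of baclofen, or 10 mg of baclofen (n=20 per group").

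Pain is measured before and after dosing. Participants do the pain battery at Session 1 without study drug and return about a week later, "where they will receive a study drug and complete the pain tasks once again". The Measurement occurrence table ticks five quantitative sensory testing (QST) tasks at both sessions: heat, cold, mechanical pressure, conditioned pain modulation and pinprick. The row "QST: Cold pressor task" is ticked for Session 1 only.

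The Introduction frames the work as early-phase: "initial evidence is needed to assess the analgesic interaction, safety, acceptability and feasibility" before a larger trial.

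The SAP is one paragraph, dated November 14, 2025 and written in the past tense. It gives within-group means and SDs for continuous variables and frequencies for categorical ones, and ends: "No analyses were conducted to compare the groups on any variable". It mentions no change score or baseline covariate, does not say whether Session 1 pain scores are among the variables summarised, and gives no analysed n. The protocol has no statistical section that fills these gaps.

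**The concern.** Whether baclofen adds to buprenorphine analgesia is a question about the difference between arms receiving buprenorphine with and without baclofen. Within-arm means do not state that difference or its uncertainty, and the SAP says explicitly that none was calculated.

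A reader with arm means, SDs and ns can work out an unadjusted difference and interval. The adjusted estimate is out of reach, because it needs participant-level data, or at least the within-arm correlation between sessions, and the SAP reports neither that correlation nor a change-score SD. With small arms, adjustment matters for two reasons: it can narrow the interval, and it corrects for chance differences in pain sensitivity that were present before any drug was given. The estimate the randomisation was set up to provide is therefore left to readers, in its less precise form.

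**Working it through.** The documents contain no power calculation, alpha, SD or effect size, so there is no stated figure to reproduce. The planned allocation is consistent: 3 × 20 = 60 in Group 2.

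**Inputs.** n = 20 per arm (protocol, Study session 2). Common SD set to 1, so results are in SD units. The Session 1 to Session 2 correlation r is not in the documents and is varied over 0, 0.3, 0.5 and 0.7. The SD is pooled over three arms: residual df = 60 − 3 = 57, or 56 with one covariate.

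**95% CI half-widths for one pairwise difference**

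- Unadjusted: t(0.975, 57) × √(2/20) = 2.002 × 0.3162 = 0.633.
- ANCOVA: t(0.975, 56) × √((1 − r²) × 2/20).
- Change score: t(0.975, 57) × √(2(1 − r) × 2/20).

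| r | Unadjusted | ANCOVA | Reduction against unadjusted | Change score |
|---|---|---|---|---|
| 0 | 0.633 | 0.633 | 0% | 0.896 |
| 0.3 | 0.633 | 0.604 | 4.6% | 0.749 |
| 0.5 | 0.633 | 0.549 | 13.4% | 0.633 |
| 0.7 | 0.633 | 0.452 | 28.6% | 0.491 |

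ANCOVA costs essentially nothing at r = 0. A change score is worse than no adjustment whenever r is below 0.5, so ANCOVA is the better choice when r is unknown.

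**Smaller analysed n.** At an illustrative 15 per arm (df 42 and 41), the half-width is 0.74 unadjusted and 0.70, 0.64 or 0.53 with ANCOVA at r = 0.3, 0.5 or 0.7.

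**Chance baseline imbalance.** The difference between two baseline means of 20 has standard error √(2/20) = 0.316 SD. P(|difference| > 0.3 SD) = 2 × (1 − Φ(0.3/0.316)) = 0.34. A gap of 0.3 SD shifts the raw Session 2 difference by an expected r × 0.3 = 0.09, 0.15 or 0.21 SD at r = 0.3, 0.5 or 0.7.

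**The case against.** The strongest case is that this is an openly descriptive pilot. The protocol names no primary endpoint, hypothesis test, alpha or power, so no pre-specified comparison was dropped. The SAP makes no efficacy claim and says plainly that groups were not compared. Readers can form the unadjusted difference, and the gain from adjustment (0% to 29%) rests on an assumed r. On this view the point is a recommendation, not a required change. It stands as a reason not to demand significance tests. It does not excuse having no estimate: the Introduction's own list of what early evidence is needed for begins with the analgesic interaction.

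Several technical points carry some weight.

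- **Analysed n.** It is unknown. The ANCOVA formula also omits a small variance term for baseline imbalance, about 1 + 1/(df − 2) with df the unadjusted residual df. At 20 per arm and r = 0 this moves 0.633 to 0.639, about 1%. At an illustrative 5 per arm the unadjusted half-width would be 1.38, against 1.46 (r = 0) or 1.39 (r = 0.3) adjusted, so adjustment would gain nothing at low r. The gains shown hold near the planned n.
- **Missing QST.** Under Study session 2, staff may skip QST for participants with intense symptoms, so values could be missing for drug-related reasons and unevenly by arm. The arm means already reported share this weakness, but counts and reasons by arm should be given.
- **Cold pain.** The bath temperature is chosen from Session 1 ratings closest to 50. If the baseline is taken at that temperature, its range is restricted. That lowers r but does not bias a randomised ANCOVA.
- **Multiplicity.** There are many outcomes with two contrasts each, so about 1 in 20 intervals would exclude zero by chance if there were no effect. This is why they must be read as estimates.

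**Conclusion.** The concern holds, and it should be fixed. The stated purpose is comparative and the design randomises to answer it, but the SAP confirms that no comparison was made and describes no use of the drug-free pain scores. This is not missing detail: following the plan exactly yields no effect estimate for the trial's question.

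Only the precision gain depends on assumptions, namely the unknown r and all 20 planned per arm being analysed. Any interval will be wide: even at r = 0.7 it is ±0.45 SD. That is a reason to report it, since otherwise readers may compare bare means without seeing how little they settle.

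**What to change.** Keep the statement that no comparison was originally made, and add a dated SAP paragraph labelled post hoc:

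1. In Group 2, for every QST outcome measured in both sessions, fit an ANCOVA of the Session 2 value on arm and the Session 1 value. Treat all outcomes equally, with no primary chosen in retrospect.
2. Report 5 mg minus placebo and 10 mg minus placebo with 95% CIs, as estimates and not confirmatory tests.
3. State the n analysed per arm and the number of outcomes examined. Add the number of participants whose Session 2 QST was skipped, with reasons, by arm.
4. State whether Session 1 pain scores were summarised.
5. Confirm whether the cold pressor task has a Session 2 value, given that the table ticks Session 1 only. If it does not, leave it out of this analysis.

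The cost is one paragraph and a set of regressions on data already collected. The drawbacks are wide intervals, many outcomes side by side, and an analysis that was not pre-specified. All three should be stated with the results.
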